4.2.4.5 Analysis of exploratory efficacy variables

Analysis of all exploratory endpoints will be performed for the Full analysis set unless otherwise specified.

The same MMRM approach (as used for the primary analysis) will be used to analyze the change in BMI, body weight percentiles and BMI percentiles from baseline Visit 3 (Week 0) to Week 28, and each intermediate visit.

The same multiple imputation ANCOVA approach (as used for the analysis of FSG and FSI) will be used to analyze change from baseline Visit 3 (Week 0) to Visit 11 (Week 28) for waist and hip circumference.

Baseline values, the values at each visit, and changes from baseline values will be summarized for BMI, percentiles of body weight, percentiles of BMI, hip circumference and waist circumference by treatment. OC summaries will be provided.

Exploratory efficacy variables will be listed.

4.2.5 Safety analyses

4.2.5.1 Adverse events

Adverse events (AE) will be classified in accordance to the MedDRA dictionary. All adverse events will be coded using the latest available version of MedDRA by the database lock.

AEs starting (or worsening) after Week 28/ED but considered by the Investigator as clinically significant and as related to study medication or study procedure, and serious adverse events (SAE) occurring within 30 days of the last administration of study medication will be recorded on the AE CRF and reported in the AE listing.

Treatment-emergent AEs (TEAE) are defined as AEs starting (or worsening) after the first dose of study medication through the end of the treatment + 1 day (or + 30 days for SAEs and other clinically significant or related AEs), including AEs collected after patients initiate glycemic rescue therapy. For patients who discontinue study medication before Week 28, the end of the treatment refers to the date of the ED visit even if last study medication was before this date.

Adverse events with a start date prior to the first administration of study medication will be classified as pre-treatment (non-treatment emergent) and will be listed only.

Post-treatment AEs are defined as AEs that start (or worsen) during the off-treatment period (safety follow-up period) defined as the day after the Visit 11 (Week 28/ED) + 1 day (or + 30 days for SAEs and other clinically significant or related AEs) to the date of completion of the safety follow-up period. As per protocol only adverse events of special interest (AESIs) will be collected in long term extension.

On-treatment AEs (TEAEs) will be summarized for 28-week treatment period as defined below.

An overall summary of number and percentage of patients experiencing at least 1 TEAE will be presented for EBID and PBO. The AE summary will include the number and percentage of patients experiencing any AE, any SAE, any AE possibly related to study drug, study procedure or study device as judged by the investigator, any AE leading to treatment discontinuation, and any fatal AE.

Additionally, all TEAEs will be summarized for each treatment group as follows:

- AEs summarized by SOC, PT, intensity (Mild, Moderate, Severe), possibly related to study drug (No, Yes) and outcome
- SAEs summarized by SOC and PT, intensity (Mild, Moderate, Severe), possibly related to study drug (No, Yes)
- AEs leading to treatment discontinuation (DAE) summarized by SOC and PT
- Frequent AEs (AE with at least 5% incidence in any treatment) summarized by preferred term
- Non-serious frequent AEs summarized by SOC and PT
- Adverse events of special interest by SOC and PT

Summaries will be presented for the treatment period (Safety analysis set).

Any AE that is recorded as the reason for study discontinuation will be considered a DAE regardless of the date recorded.

Potentially immune-related AEs will be listed and identified using the PTs given in [Appendix 5](#).

Tables of key patient information for SAEs and AEs leading to discontinuation of study medication will be provided. Adverse events will be listed.

The number of AEs and number of SAEs will be summarized for the treatment period.

The denominator for summaries will be the number of patients included in the analysis set by treatment group and total.

Selected AEs have been identified as AESIs. During the safety follow-up period, only AESIs will be recorded in the CRF.

The AESIs recorded are as follows:

- Hematological malignancies
- Thyroid neoplasms
- Pancreas neoplasms
- Aplastic anemia
- Pancreatitis
- Pregnancy and pregnancy outcomes (including congenital anomalies)

This list may be updated if additional AESIs are identified. All AESIs will be listed.

AESIs will be summarized by system organ class (SOC), PT, intensity (Mild, Moderate, Severe), seriousness and outcome by the actual treatment during the randomized period for the Safety follow-up analysis set.

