#### 7.4. Discontinuations

The criteria for enrollment must be followed explicitly. If a patient who does not meet enrollment criteria is inadvertently enrolled, that patient will continue in the study unless, in the opinion of the Sponsor's physician responsible for the study, the patient should be discontinued for safety reasons. The Sponsor or its designees must be contacted.

In addition, patients will be discontinued from the treatment period of the study in any of the following circumstances:

- if the patient experiences a loss of glycemic control, as evidenced by:
  - increase in absolute HbA1c  $\geq 0.5\%$  from baseline at 2 consecutive scheduled visits which are at least 1 month apart, prior to study completion
  - fasting blood glucose  $>250$  mg/dL (13.9 mmol/L) or non-fasting glucose  $>300$  mg/dL (16.7 mmol/L) for 4 days in a 7-day period as measured by SMBG. The patient will return to the clinic for a confirmatory fasting glucose, if possible, or a non-fasting glucose. If by local laboratory measurement a fasting glucose is  $>250$  mg/dL (13.9 mmol/L) or a non-fasting glucose is  $>300$  mg/dL (16.7 mmol/L), the patient will be discontinued from the study
- if a female patient becomes pregnant
- if the patient misses more than 10 consecutive days of study therapy
- if the patient misses more than 10 consecutive days of oral antidiabetes therapy
- if metformin or an SU is added or altered for more than 10 consecutive days or 10 days in a 30-day period after study entry
- if a patient uses excluded concomitant medications ([Section 7.2](#), Exclusion Criteria)

- if the investigator decides that the patient should be withdrawn. If this decision is made because of a serious adverse event or a clinically significant laboratory value, the study drug is to be discontinued and appropriate measures are to be taken. The Sponsor or its designee is to be notified immediately
- if the patient or attending physician requests that the patient is withdrawn from the study
- if the investigator or the Sponsor, for any reason, stops the study or stops the patient's participation in the study.

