Due to the availability of other more conveniently administered therapies e.g. oral, once daily (QD), or once weekly (QW), recruitment to this study has been slow/difficult despite extensive efforts by the sponsor. The planned number of patients will take unreasonably long to recruit so a decision was made with agreement by the European Medicines Agency and Food and Drug Administration to stop recruitment and to pool patients from both exenatide arms and compare the pooled arm with placebo. With a total of 122 patients randomized (Total EBID:Placebo 2:1), the study should have approximately 87% power to detect a difference between Total EBID and placebo assuming the true mean changes in HbA1c are -0.7, -0.5, and 0 for patients receiving exenatide 10 µg BID, exenatide 5 µg BID, and placebo BID, respectively. The combined effect of the Total EBID doses compared to placebo (mean difference) is assumed to be -0.6 with a common standard deviation of 1% at the 5% significance level without consideration of patient discontinuation and impact on effect size. An assumed effect size of -0.455 was considered in power calculation.

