3.6.6 Study periods

The following definitions will be used to assign data to the correct study period. For details on which data will be presented in outputs for each endpoint, refer to Section 4.2.

Pre-treatment period: defined as the period prior to the date of the first dose of randomized study medication. All data for patients who do not receive randomized study medication will be considered pre-treatment.

Treatment period: defined as the date of first dose of randomized study medication to date of the Week 28 visit, or the ED visit for patients who discontinue the study prior to Week 28.

Safety follow-up period: defined as the day after the Visit 11 (Week 28) visit, or the day after the ED visit for patients who discontinue the study prior to Visit 11 to the date of completion of the Safety follow-up study (typically after 3 years or once the patient has a height difference of less than 5 mm between two 6-month interval visits). The safety follow-up period will only be defined for patients who enter the safety follow-up period.

See Section 4.1.3 for details on missing data handling.

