4.2.5.2 Hypoglycemic episodes

Confirmed hypoglycemic episodes will be defined as follows:

Minor hypoglycemia:

- Any time a patient feels that he or she is experiencing a sign or symptom associated with hypoglycemia that is either self-treated by the patient or resolves on its own and
- Has a concurrent fingerstick blood glucose <3.0 mmol/L (54 mg/dL).

Major hypoglycemia:

- any episode with symptoms consistent with hypoglycemia resulting in loss of consciousness or seizure that shows prompt recovery in response to administration of glucagon or glucose or
- documented hypoglycemia (blood glucose <3.0 mmol/L [54 mg/dL]) requiring the assistance of another person because of severe impairment in consciousness or behavior (regardless of whether symptoms of hypoglycemia are detected by the patient).

Episodes will be categorized into major or minor following medical review of the hypoglycemic data by an AstraZeneca or IQVIA physician.

Incidence of hypoglycemic episodes will be summarized by whether they are major or minor and by when the episodes occurred (night-time will be defined to be between 11pm and 5 am) using frequencies and percentages of patients with at least one episode of hypoglycemia occurring during the study. The number of episodes per patient will be classified into categories (0, 1 to 2, 3 to 4, ≥ 5), and summarized using frequencies by treatment group and visit for the Safety analysis set.

Similar analyses will be performed for confirmed hypoglycemic episodes (those with a blood glucose record) and unconfirmed hypoglycemic episodes (those reported into study database without corroborating blood glucose record).

Minor and Major hypoglycemia rate (adjusted for duration of exposure to study drug therapy = the date of last dose of IP – date of first dose of IP +1) will be summarized by treatment.

The number and percentage of patients with any confirmed and unconfirmed hypoglycemic episodes will also be summarized by baseline sulfonylurea use (yes/no) and treatment.

Hypoglycemic events will be listed.

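### Withdrawal for loss of glycemic control shortens AE observation in a way that depends on outcome, yet SAP 4.2.5.1 plans only crude TEAE percentages and bare event counts

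*SAP*

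**What the plan says.** **Who leaves.** Protocol 7.4 discontinues a patient "if the patient experiences a loss of glycemic control, as evidenced by" either an HbA1c at least 0.5% above baseline at two consecutive scheduled visits at least a month apart, or home glucose readings above set limits that a local laboratory confirms. Protocol 6.1.7 and SAP 4.2.4.4 repeat the rule.

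**When observation stops.** Under SAP 3.6.6 the treatment period runs to the Week 28 visit, "or the ED visit for patients who discontinue the study prior to Week 28". SAP 4.2.5.1 counts an AE as treatment-emergent up to one day after that point. SAEs and other clinically significant or related AEs get 30 days. In the safety follow-up only AEs of special interest are recorded.

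**How AEs are summarized.** In SAP 4.2.5.1: "An overall summary of number and percentage of patients experiencing at least 1 TEAE will be presented for EBID and PBO". Also: "The number of AEs and number of SAEs will be summarized for the treatment period". The denominator is the number of patients in the analysis set. No AE rate per unit of time is planned.

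**What is adjusted.** SAP 4.2.5.2 does use time for one outcome: "Minor and Major hypoglycemia rate (adjusted for duration of exposure to study drug therapy", taken from first to last dose. Duration of exposure is tabulated separately under SAP 4.2.3.

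**The concern.** The withdrawal rule responds to the outcome the drug is meant to change. If exenatide lowers HbA1c as assumed, the rule removes more placebo patients, and their later ordinary AEs are not recorded. A crude percentage then compares arms observed for different lengths of time. The bare counts have a simpler problem that needs no modelling: at about 81 versus 41 patients, equal risk gives about 81/41 = 2.0 times as many events on exenatide.

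These tables are the trial's main between-arm evidence on ordinary AEs in adolescents, and safety and tolerability is a stated secondary objective. The SAP already accepts exposure adjustment for hypoglycemia, so its absence for other AEs is a gap within the same section.

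**Working it through.** **Inputs from the documents**
- SAP 1.3, means: "true mean changes in HbA1c are -0.7, -0.5, and 0 for patients receiving exenatide 10 µg BID", 5 µg and placebo in that order.
- SAP 1.3, pooled effect: "The combined effect of the Total EBID doses compared to placebo (mean difference) is assumed to be -0.6".
- SAP 1.3, variability: "common standard deviation of 1% at the 5% significance level".
- SAP 1.3: 122 patients at 2:1, about 81 and 41; stated power about 87%.
- Protocol Attachment 1: post-baseline HbA1c at Weeks 4, 12, 20 and 28. The pairs that can shorten treatment are Weeks 4/12 and 12/20.

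**Assumptions not in the documents**
- HbA1c change is normal with SD 1 at every visit.
- Between-visit correlation is 0.5, 0.7 or 0.8, the same for all pairs.
- The exenatide effect is full (−0.6) throughout, or half at Week 4 and full afterwards.
- Exit is one week after the triggering visit (Week 13 or 21).
- No other cause of dropout. The home-glucose rule cannot be computed from the documents.

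**Step 1. Reproduce the stated power.** 0.6/√(1/81 + 1/41) = 3.13. The noncentral t with 120 df gives 87.4%, in line with about 87%.

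**Step 2. One visit.** P(change ≥ 0.5) is 30.9% on placebo, 15.9% on 5 µg and 11.5% on 10 µg. The two doses average 13.7%, so the ratio is 30.9/13.7 = 2.25.

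**Step 3. Two consecutive visits, by simulation.** Let p₁ be the proportion leaving after Weeks 4/12 and p₂ the proportion leaving after Weeks 12/20. Mean weeks observed = 28 − 15p₁ − 7p₂.

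| Correlation | Arm | Withdrawn | Mean weeks | Time lost |
|---|---|---|---|---|
| 0.5 | placebo | 22.1% | 25.15 | 10.2% |
| 0.5 | exenatide, full / half at Week 4 | 7.4% / 8.5% | 27.08 / 26.86 | 3.3% / 4.1% |
| 0.7 | placebo | 24.5% | 24.71 | 11.8% |
| 0.7 | exenatide, full / half | 9.1% / 10.3% | 26.81 / 26.56 | 4.2% / 5.1% |
| 0.8 | placebo | 25.8% | 24.45 | 12.7% |
| 0.8 | exenatide, full / half | 10.1% / 11.3% | 26.64 / 26.39 | 4.8% / 5.7% |

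Example at correlation 0.5, full effect:
- Placebo: 28 − 15(0.1634) − 7(0.0575) = 25.15 weeks.
- Exenatide: 28 − 15(0.0499) − 7(0.0240) = 27.08 weeks.
- 25.15/27.08 = 0.929, so placebo has 7.1% less time. Across the table the shortfall is 6.4% to 8.2%.

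**Step 4. Effect on the crude percentage.** Give both arms the same constant hazard, with 28-week risk R. Risk to week w is 1 − (1 − R)^(w/28). Crude incidence = (1 − p₁ − p₂)R + p₁·risk(13) + p₂·risk(21).
- R = 20%, same example: risk(13) = 9.8%, risk(21) = 15.4%. Placebo 18.1%, exenatide 19.4%: a gap of 1.3 points. Across the table, 1.15 to 1.5.
- R = 60%, same example: risk(13) = 34.7%, risk(21) = 49.7%. Placebo 55.3%, exenatide 58.5%: a gap of 3.2 points. Across the table, 2.8 to 3.7.

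**Step 5. Sensitivity.**
- Correlation 0.3 to 0.9, including AR(1) structures and a slower onset: the withdrawal ratio runs from 1.9 to 3.4.
- Smaller SDs at Weeks 4, 12 and 20 (0.5, 0.8, 0.9; assumed), full effect: placebo time lost falls to about 7–9%. The gaps are 1.1–1.3 points at R = 20% and 2.6–3.3 points at R = 60%.

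**The case against.** **Direction.** A reader might infer that placebo incidence will be understated and the exenatide excess overstated. The documents do not settle this. Their only discontinuation figure is about 23%, for the exenatide arms (Protocol 11.1, SAP 1.3), with none for placebo. Spread evenly over 28 weeks, 23% gives 28 × 0.77 + 14 × 0.23 = 24.8 weeks on exenatide. That lies inside the 24.4–25.2 weeks that the HbA1c rule alone leaves on placebo. This objection stands in full.

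**Size.** One might quote the 10–13% of placebo time lost as the bias. That is a one-arm loss of time and ignores the 3–6% lost on exenatide. The bias in the planned percentage is 1 to 4 points. The 95% half-width for a difference, 1.96√[p(1−p)(1/81 + 1/41)], is 15 points at p = 20% and 18 at p = 60%, in tables with no planned test. This stands too.

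**Other planned tables.** It would be wrong to say that the outputs cannot separate loss of control from intolerance, or that event counts cannot be put on a common scale. Discontinuation reasons (SAP 4.2.1.1), loss-of-control withdrawals by visit (4.2.4.4), AEs leading to discontinuation (4.2.5.1) and exposure duration (4.2.3) are all reported by arm. Mean exposure times n gives approximate person-time. But that exposure runs from first to last dose, while the TEAE window runs to the ED visit. First-event incidence cannot be rebuilt from it.

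**On-treatment definition.** The unrecorded weeks are off study drug, and stopping ordinary AEs there is conventional. Collection does not stop altogether: SAEs and related events run 30 days further, and special-interest events continue in follow-up. Completers get the same extensions, so the imbalance remains.

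**Early events.** The HbA1c rule cannot act before Week 12. Events clustered at the start, such as nausea, are little affected, and a rate would handle them worse than a percentage.

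**Conclusion.** The point holds as a modest gap in reporting. Ordinary AE observation ends with an outcome-driven withdrawal, observation time can differ by arm, and SAP 4.2.5.1 offers no summary that allows for it.

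From the HbA1c rule alone, about 22–26% of placebo and 7–11% of exenatide patients leave by Week 20. Placebo has about 6–8% less observation time, and its crude TEAE incidence looks lower by about 1–1.5 points (risk 20%) to 3–4 points (risk 60%). These are derived figures; the plan states no loss-of-control rate. They rest on the assumed correlation, SD 1 at each visit, onset of effect, constant equal hazards and no other dropout.

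The documents do not show that the final AE comparison will favor either arm. That uncertainty is itself a reason to show person-time. The change is worth making; the crude tables are not unusable without it.

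**What to change.** In SAP 4.2.5.1, keep the percentages and the event counts (Protocol 11.2.8.2 promises event frequency) and add beside them:

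- Event rates per 100 patient-years for AEs and SAEs.
- Exposure-adjusted incidence for any TEAE, SAEs, AEs leading to discontinuation and frequent AEs: patients with a first event divided by patient-years at risk, censored at first event.
- The EBID–placebo difference with 95% CI for the overall categories only. With about 41 placebo patients, intervals for each preferred term would add little.

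State the time at risk by event type:

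- *Ordinary TEAEs:* first randomized dose to Week 28/ED + 1 day. Events in the later 30-day extension are left out of the rate.
- *SAEs:* first randomized dose to the end of SAE collection. The text must first be reconciled. Protocol 9.2.1.1 and one paragraph of SAP 4.2.5.1 count 30 days from the last dose. The TEAE definition counts 30 days from the end of treatment, which for early discontinuers is the ED visit even if dosing stopped earlier.

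Cost: SAP wording and extra table columns. The dose, visit and AE onset dates are already collected. The downside is that a rate assumes a roughly constant hazard. Early events divided by shortened placebo time would inflate the placebo rate, so a footnote should direct readers to the percentages for events such as nausea.

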4.2.5.2 Hypoglycemic episodes

Confirmed hypoglycemic episodes will be defined as follows:

Minor hypoglycemia:

- Any time a patient feels that he or she is experiencing a sign or symptom associated with hypoglycemia that is either self-treated by the patient or resolves on its own and
- Has a concurrent fingerstick blood glucose <3.0 mmol/L (54 mg/dL).

Major hypoglycemia:

- any episode with symptoms consistent with hypoglycemia resulting in loss of consciousness or seizure that shows prompt recovery in response to administration of glucagon or glucose or
- documented hypoglycemia (blood glucose <3.0 mmol/L [54 mg/dL]) requiring the assistance of another person because of severe impairment in consciousness or behavior (regardless of whether symptoms of hypoglycemia are detected by the patient).

Episodes will be categorized into major or minor following medical review of the hypoglycemic data by an AstraZeneca or IQVIA physician.

Incidence of hypoglycemic episodes will be summarized by whether they are major or minor and by when the episodes occurred (night-time will be defined to be between 11pm and 5 am) using frequencies and percentages of patients with at least one episode of hypoglycemia occurring during the study. The number of episodes per patient will be classified into categories (0, 1 to 2, 3 to 4, ≥ 5), and summarized using frequencies by treatment group and visit for the Safety analysis set.

Similar analyses will be performed for confirmed hypoglycemic episodes (those with a blood glucose record) and unconfirmed hypoglycemic episodes (those reported into study database without corroborating blood glucose record).

Minor and Major hypoglycemia rate (adjusted for duration of exposure to study drug therapy = the date of last dose of IP – date of first dose of IP +1) will be summarized by treatment.

The number and percentage of patients with any confirmed and unconfirmed hypoglycemic episodes will also be summarized by baseline sulfonylurea use (yes/no) and treatment.

Hypoglycemic events will be listed.

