1.3 Number of patients

Approximately 195 patients diagnosed with type 2 diabetes were planned to be enrolled. Approximately 65 patients were to be randomized to receive placebo and 130 patients were to be randomized to receive exenatide (65 per exenatide treatment arm). A sample of 65 patients per treatment arm would provide >95% power to reject the null hypothesis of no difference among treatments assuming true mean changes in HbA1c of -0.7, -0.5, and 0 for patients receiving exenatide 10 µg twice daily, exenatide 5 µg twice daily, and placebo twice daily, respectively (based on results of previous Studies 2993-112, CCI, H8O-MC-GWAA, H8O-MC-GWAD). This power computation also assumes a common standard deviation of 1.0% and a two-sided significance level of 0.05. Assuming the same true mean changes in HbA1c, common standard deviation, and two-sided significance level, 65 patients per treatment arm would also provide >95% power to detect a difference between 10 µg exenatide twice daily and placebo

treatments, and 80% power to detect a difference between 5 µg exenatide twice daily and placebo with a Fisher Protected Testing procedure (Hayter 1986).

Due to an approximate 23% discontinuation rate in the exenatide arms (based on results from 2993-112), 65 patients randomized per treatment arm would be enough to observe 50 completers per treatment arm. Patients will be eligible to participate if they are not achieving adequate glycemic control (i.e. HbA1c at screening is 6.5% to 10.5%, inclusive) with metformin, an SU, or metformin and an SU, or diet and exercise only. Patients will be stratified to treatment assignment based on diabetes therapy at enrolment and screening HbA1c. The three-arm design was intended to allow comparison of exenatide at doses of 5 µg twice daily and 10 µg twice daily with placebo twice daily.

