4.1.1 Statistical notations and presentations

Although patients randomly assigned to placebo will be assigned to take the volume equivalent to 5 µg exenatide twice daily or to take the volume equivalent to 10 µg exenatide twice daily, all patients assigned to placebo will be combined into 1 group for analysis purposes. Descriptive summaries will present treatment groups separately, as follows:

5 µg EBID	10 µg EBID	Total EBID	Placebo	Total
EBID Exenatide twice daily				

Total EBID is the pool of the 10 µg and 5 µg EBID doses. Total (over all treatments) will not be included in efficacy and safety endpoint outputs.

Summaries including data from the safety follow-up period will be presented by the actual treatment group during the randomized period.

All efficacy and safety variables will be summarized using descriptive statistics as appropriate. Continuous variables will be summarized by descriptive statistics including n (number of patients with available data), arithmetic mean, standard deviation (SD), median, minimum value and maximum value. The mean and median will be presented with one more decimal place than the original data; the standard deviation with two more decimal places than the original data; and minimum and maximum values with the same number of decimal places as the original data. Categorical variables will be summarized using frequency tables (number of patients and percentage of patients in each category). Unless otherwise stated, percentages will be calculated out of the analysis set total for the treatment group. Percentages will be rounded to one decimal place.

For log transformed data, the following descriptive statistics will be presented: n (number of patients with available data), geometric mean, geometric coefficient of variation (GCV%), geometric standard deviation factor (GSD), arithmetic mean, standard deviation, coefficient of variation (CV%), median, minimum and maximum value.

GCV (%) will be calculated as

$$100 \cdot \sqrt{(\exp(s^2) - 1)}$$

where s is the SD of the data on a log scale.

Individual data will be presented in patient listings. All patient data listings will be sorted by treatment and patient identifier ID. The first 3 digits of the patient ID denotes the center number and the next 4 digits denotes the individual patient number.

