4.3 Conventions

All visits scheduled during the 28-week treatment period should occur within ± 7 days of the scheduled date relative to Visit 3 (Week 0) per the CSP. All visits during the safety follow-up period should occur within 6 months ± 2 weeks of the previous visit.

Patients do not always adhere strictly to the visit timing in the CSP. Therefore, the designation of visits during the treatment period will be based on the day of evaluation relative to the start of the treatment period (day of study medication = Day 1) rather than the nominal visit recorded in the CRF. Designation of visits during the safety follow-up period will be based on the day of evaluation relative to the last date of the treatment period (Visit 11/ED).

To assign a measurement to a Week t during the study, the first step is to select all measurements falling within the study period. Mutually exclusive relative day windows are used to determine the Week t measurement. These relative day windows are defined to provide derived visits that correspond to the post-baseline time points specified in the CSP. Visit windows are listed below.

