4.3.2 Visit assignment for safety variables

Table 7 Visit Windows: Antibodies to exenatide and vital signs

Visit	Week	Period	Target Day	Day range
3	0	TP	1	Baseline
5	4	TP	29	2-56
7	12	TP	85	57-112
9	20	TP	141	113-168
11	28	TP	197	169-last day of TP

TP: Treatment period.

Table 8 Visit Windows: Body weight, height, BMI and Tanner pubertal assessment

Visit	Week	Period	Target Day	Day range
3	0	TP	1	Baseline
5	4	TP	29	2-56
7	12	TP	85	57-112
9	20	TP	141	113-168
11	28	TP	197	169-last day of TP
801	+26	SFU	+183	last day of TP+1-273
802	+52	SFU	[contact]	+78	SFU	[contact]	+104	SFU	[contact]	+130	SFU	[contact]/ED	+156	SFU	+1093	1002-last day of SFU

TP: Treatment period. SFU: Safety follow-up period (+ denotes relative to Visit 11/ED)

Table 9 Visit Windows: Laboratory data, ECG, waist circumference and hip circumference

Visit	Week	Period	Target Day	Day range
3	0	TP	1	Baseline
11	28	TP	197	2-last day of TP
801	+26	SFU	+183	last day of TP+1-273
802	+52	SFU	[contact]	+78	SFU	[contact]	+104	SFU	[contact]	+130	SFU	[contact]/ED	+156	SFU	+1093	1002-last day of SFU

TP: Treatment period. SFU: Safety follow-up period (+ denotes relative to Visit 11/ED). Only CEA and calcitonin measured during SFU

Table 10 Visit windows: Hypoglycemic episodes

Visit	Week	Period	Target Day	Day range
3	0	TP	1	Baseline
4	2	TP	15	2-21
5	4	TP	29	22-42
6	8	TP	57	43-70
7	12	TP	85	71-98
8	16	TP	113	99-126
9	20	TP	141	127-154
10	24	TP	169	155-182
11	28	TP	197	183-last day of TP

TP: Treatment period.

Collected at clinic visits but discussed during telephone visits

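### The by-visit hypoglycemia table uses windows of unequal length with no exposure adjustment, so a constant rate would show a false rise at Week 8 and a false fall at Week 28.

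*SAP*

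**What the plan says.** SAP 4.2.5.2 groups patients by number of hypoglycemic episodes (none, 1-2, 3-4, 5 or more). The groups are "summarized using frequencies by treatment group and visit for the Safety analysis set", and similar analyses follow for confirmed and unconfirmed episodes. The same section plans minor and major rates adjusted for exposure, by treatment only. No rate by visit is planned.

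The visits are defined in SAP 4.3.2, "Table 10 Visit windows: Hypoglycemic episodes". The rows are Days 2-21, 22-42, 43-70, 71-98, 99-126, 127-154 and 155-182, then Day 183 to the last day of the treatment period. SAP 3.6.6 has that period "defined as the date of first dose of randomized study medication to date of the Week 28 visit", or to the early discontinuation visit. SAP 4.3 adds the tolerance: "All visits scheduled during the 28-week treatment period should occur within ± 7 days of the scheduled date".

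For denominators, SAP 4.1.1 sets the default that "percentages will be calculated out of the analysis set total for the treatment group", unless stated otherwise, and 4.2.5.2 states nothing else for this table. SAP 4.1.3.3 restricts safety analyses to observed cases, without saying what that does to a by-visit denominator. SAP 1.3 plans for an "approximate 23% discontinuation rate in the exenatide arms".

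**The concern.** Similar windows serve weight and antibodies in SAP 4.3.2, where they pick a single assessment and their length matters little. Episode counts accumulate over time, so a shorter window holds fewer episodes at the same underlying rate. A row that also keeps discontinued patients in its denominator is lowered further.

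The by-visit table is the only planned summary of hypoglycemia over study time. Its lengths change at two places where a reader would look for a pattern. One is the move from the Week 4 row to the Week 8 row, the first row lying wholly after the nominal date of the step to 10 µg. The other is the end of treatment. An artificial rise followed by an artificial fall could be taken for a dose effect that later wears off.

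A smaller gap concerns Day 1. The first post-baseline window opens on Day 2, but SAP 4.3 makes the day of first study medication Day 1. Protocol 6.1.3 places that dose on the evening of Visit 3, or at the clinic that day for patients in the pharmacokinetic addendum. An episode later on Day 1 belongs to no post-baseline row.

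**Working it through.** **Inputs.** Window limits: SAP Table 10. Target day of Visit 11: Day 197 (Table 10), with ±7 days (SAP 4.3), so Day 190 to 204. Discontinuation: 23% (SAP 1.3). Assumptions not in the documents: windows apply to episode dates, episodes follow a constant Poisson rate, and dropout is exponential, reaching 23% by Day 197.

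**The plan's own figure.** 65 × (1 − 0.23) = 50.05, which reproduces the 50 completers per arm in SAP 1.3. The documents give no by-visit hypoglycemia figure to check.

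**Step 1: window length.** Length = last day − first day + 1. The final window is 197 − 183 + 1 = 15 days on target, 8 days if Visit 11 is on Day 190, and 22 days if it is on Day 204.

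**Step 2: fall in the Week 28 row, Visit 11 on Day 197.** With a constant rate and the full Safety set as denominator, expected episodes in a row are proportional to the sum of S(t) over its days. S(t) is the share of patients still in the study: S(t) = 1 without dropout, or S(t) = exp(−ht) with h = −ln(0.77)/197. Fall = 1 − (Week 28 sum ÷ comparison sum).

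| Comparison row | Days | Length | Fall, no dropout | Fall, 23% dropout |
|---|---|---|---|---|
| Week 2 | 2-21 | 20 | 25.0% | 40.8% |
| Week 4 | 22-42 | 21 | 28.6% | 42.1% |
| Week 8 | 43-70 | 28 | 46.4% | 55.1% |
| Week 12 | 71-98 | 28 | 46.4% | 53.4% |
| Week 16 | 99-126 | 28 | 46.4% | 51.7% |
| Week 20 | 127-154 | 28 | 46.4% | 49.8% |
| Week 24 | 155-182 | 28 | 46.4% | 47.9% |

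Without dropout, the fall against a 28-day row is 1 − 15/28 = 46.4%. The ceiling, with nobody lost in the 28-day row and 77% left at Week 28, is 1 − 15 × 0.77/28 = 58.8%.

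**Step 3: Visit 11 off target.**
- Day 204 (22 days): the fall against the 28-day rows is 1 − 22/28 = 21.4% without dropout, and 24.0% to 34.5% with it. Against Week 2 the result runs from a 10% rise (22/20) without dropout to a 13.6% fall with it.
- Day 190 (8 days): the fall against the 28-day rows is 1 − 8/28 = 71.4% without dropout, and 72.1% to 76.0% with it.

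**Step 4: Week 4 to Week 8.** Without dropout, 28/21 = 1.33, a rise of 33%. With 23% dropout, from the table, (1 − 0.421)/(1 − 0.551) = 0.579/0.449 = 1.29, a rise of 29%.

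**Step 5: patients rather than episodes.** The table counts patients by category, so the share with at least one episode was also computed (Visit 11 on Day 197, against the 28-day rows, with and without 23% dropout). The fall is about 45-55% at up to 1 episode per patient-year, 41-50% at 6 per year and 26-38% at 24 per year. These rates are assumed.

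**Step 6: what a correction does.** Counting only patients still at risk, with nothing else changed, leaves a fall of 1 − 15/28 = 46.4% against the 28-day rows. Dividing episodes by patient-days in each window gives a ratio of 1.00 between all rows under a constant rate.

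**The case against.** The strongest objection is that SAP 4.3 assigns visits by day of evaluation, and the Table 10 footnote says episodes are collected at clinic visits and only discussed by telephone. Protocol Attachment 1 transfers them from diaries at Visits 3, 5, 7, 9 and 11, or at early discontinuation. If the evaluation day governs, the Visit 11 row covers diary time since Visit 9 and the Week 28 fall disappears. Against this, Table 10 has rows for telephone Visits 4, 6, 8 and 10, which make little sense unless episodes are placed by their own date. The episode-date reading is the more natural one, but the SAP does not state it.

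The denominator is also open. The rule in 4.1.1 is a default, and the observed-case sentence in 4.1.3.3 can be read as removing patients who are no longer seen. A reader might infer that dropouts are certainly counted as having no episodes; the text does not settle that. The 46% from window length does not depend on it.

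The table is descriptive and carries no test. Protocol 11.2.8.4 asks for distribution, incidence and an exposure-adjusted rate by treatment, not for a by-visit display. Overall incidence and the overall rate are untouched. Day 1 episodes are not lost either: they remain in the overall incidence, the rate and the listing. These points limit the consequence but do not remove the artefact.

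**Conclusion.** The point holds as a distortion of comparisons across visits within an arm. The headline size, about 46% from window length and about 48-55% with dropout, applies to the 28-day rows, a low event rate and Visit 11 on Day 197. The dropout part also needs the whole-set denominator and the 23% planning figure, which SAP 1.3 gives for the exenatide arms only.

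A reader might infer that the Week 28 row always falls by half or more. The documents do not support that: against Weeks 2 and 4 the fall is 25-42%, a late Visit 11 reduces it to 21-35% against the 28-day rows, and frequent episodes shrink it further. An early Visit 11 enlarges it. A reader might also infer a bias between arms. Window length acts alike on all arms in the same row, so such a bias needs dropout or visit timing that differs by arm, and neither document reports that.

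This is an inexpensive correction to a descriptive safety table and should be made. It does not bear on the primary analysis.

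**What to change.** In SAP 4.2.5.2:

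- State that the Table 10 windows apply to the date of the episode.
- Keep the planned count categories, but use as denominator the patients still under observation in each window. Say how this fits with the default in 4.1.1 and the observed-case rule in 4.1.3.3.
- Add, for each window and arm, patient-days observed and episodes per patient-day. Days observed run from the window start to the earlier of the window end and the patient's last hypoglycemia collection. This item is essential, because the denominator change alone leaves the window-length artefact in place.
- In Table 10, open the first post-baseline window at the first randomized dose on Day 1.

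The cost is SAP wording, one derived variable (days observed per window) and a slightly larger descriptive table. No new data are needed.
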